2.3 Incorporation of lessons learned to date

As of this revision (Version 8), we have accrued 7 patients into Stage 1 of the protocol (five in group 1, and two in group 2). In reviewing our data to date, we conclude that the residual alignment error as calculated using either the bony fusion algorithm or implanted fiducial methods are in good agreement, with no significant difference between the methods (Figure 1).

[figure not shown]

Figure 1: Left panel - Examining the differences in the calculated error in each dimension using both fusion and fiducials reveals good agreement (average difference near zero). Right panel - RMS analysis demonstrates no statistical or clinically meaningful difference.

Extending our analysis, we have performed offline 6D fusions of the CT-on-rails-datasets with the simulation data sets, and conclude that fiducials are no better than the bony fusion algorithm for correcting rotational error (Figure 2).

[figure not shown]

Figure 2: Using offline 6 dimensional fusion, an accurate assessment of residual rotational error can be performed. RMS analysis demonstrates no significant difference in performance between the two approaches.

An additional development has been the migration of our spinal SBRT treatments to a new linear accelerator, with upgraded capabilities (e.g. 6D robotic couch correction, cone-beam CT, and improved fusion algorithm). These new capabilities will further improve the overall accuracy of patient setup with respect to rotational error. As we have demonstrated that any difference between the fusion approach and the fiducial approach has thus far been too small to detect, we believe that the improved platform would further close the hypothetical gap between the approaches, and that we will not be able to observe it.

Thus, going forward, we will:

- Remove the fiducial component from the protocol

- Prospectively enroll additional patients (without the need for fiducials) to characterize the accuracy of the new treatment platform, including a group of patients with tumors in the cervicothoracic junction (who were not originally included because of challenges with fiducial placement)
- Perform a retrospective study of setup accuracy in patients with cervicothoracic junction tumors as historical controls

3.0 Patient Eligibility

3.1 Inclusion Criteria

Stage 1:

- 1) Greater than or equal to 18 years of age
- 2) Pathologically confirmed diagnosis of cancer, including, but not limited to non-small cell lung cancer, breast, prostate, renal cell, melanoma, gastrointestinal, sarcoma, thyroid, head and neck primary, and carcinoma of unknown primary
- 3) Signed informed consent

Stage 2:

- 1-3 above, and
- 4) Patients undergoing single fraction spinal SBRT

3.2 Exclusion Criteria

Stage 1:

- 1) Patient with radiosensitive histologies (lymphoma, multiple myeloma, small cell carcinomas, germ cell tumors)
- 2) Extensive (> 50%) height loss of the involved vertebral body

3) Inability to tolerate lying flat on treatment table for greater than 30 minutes

4) Pregnancy

3.3 Additional exclusion criteria, Stage 2

1) Prior irradiation of the spine site and level to be treated

2) Patients with primary disease arising in the posterior elements of the VB in question

3) History of Barrett's esophagus, esophageal webbing, stricture, or fistula

4) Prior radiation to the esophagus

4.0 Pretreatment evaluation

1) Patients will undergo a thorough history and physical.

2) Patient cases will be reviewed at a multidisciplinary stereotactic spine conference to discuss dose, fractionation and radiosurgical target.

3) An MRI of the spine must be performed within 4 weeks of registration.

5.0 Treatment Plan

5.1 Summary of study design

Our overall study plan consists of two stages. In the first stage, we will seek to characterize the accuracy of our new treatment platform and perform analysis of the ExacTrac positioning system.. Four dimensional CT datasets are recommended for simulation will also allow us to use data from this portion of the protocol to characterize the degree to which organ at risk (OAR) motion is relevant at each spinal level. In this stage, we will now close accrual to

Groups 1 (T4-T12 with fiducials) and 2 (L1-L5 with fiducials) and begin enrollment in three new groups of 10 patients each:

Group 5: tumors from C5-T3

[figure not shown]
Group 6: T4-T12

Group 7: L1-L5

Patients in groups 5-7 will not undergo gold fiducial placement. In this stage of the study patients will be treated with the standard dose constraints to normal tissues.

In the second stage, we will seek to characterize the tolerance of the esophagus to hypofractionated radiation doses through prospective constraint relaxation and toxicity monitoring. In this stage, we will seek to accrue 20 additional patients in two groups of 10, to be filled sequentially with progressive constraint relaxation (Group 3: T4-T10 / constraint level 2, Group 4: T4-T10 / constraint level 3). The data collected from Group 1 in the first stage of the protocol will give us data on the dose delivered to the esophagus under our current practice guidelines (which are commensurate with the guidelines of the multicenter RTOG 06-31 trial (12), and will serve to verify the safety of our current practice. The second stage of the protocol will accrue in parallel with stage 1. Once Group 3 has completed accrual, patients will be prospectively monitored for a period of 3 months for signs of adverse esophageal toxicity before Group 4 opens. The dose constraints that will be used for Groups 3 allow higher dose than is used in our practice at MD Anderson, but comply with published guidelines for SBRT treatment (29). The dose constraints for Group 4 represent a modest increase of esophageal dose maximums from these guidelines, but the maximum esophageal dose falls well under the maximum allowed on the current RTOG 0813 trial (37). Detailed dose constraint parameters are

enumerated in Section 5.6.2, below. In total, the study seeks to accrue 40 patients. The overall trial schema is summarized below.

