5.5 Dose constraints

5.5.1 Esophageal dose constraints

The esophageal dose constraints for the protocol are summarized in Table 3. In stage 1, focusing on use of the fiducial system, patients dispositioned to undergo single and multi-fraction treatments will be enrolled, using our current practice guidelines for esophageal dose

constraints. For single fraction treatments, 5 cc of the esophageal volume must receive less than 12 Gy and the maximum dose (defined as that delivered to less than 0.01 cc of the esophageal volume) must not exceed 16 Gy. For 3 fraction treatments, 5 cc of the esophageal volume must receive less than 15 Gy and the maximum dose received must not exceed 21 Gy. The dose to 1cc of esophageal volume will be recommended, but not required, to be under 14 and 17 Gy respectively.

In stage 2 of the protocol, only patients receiving single fraction treatment will be eligible. Group 3 patients will be planned with constraints of 14.5 and 19 Gy to 5cc and 0.01 cc's respectively, with a recommended dose of 17 Gy as a 1 cc constraint. These dose constraints represent published guidelines issued by other groups with expertise in stereotactic radiation treatment, and will be prospectively validated in our system. Once Group 3 accrual and monitoring has been completed, we will enroll patients to Group 4, with 5 cc and 0.01 cc constraints of 18 Gy and 22 Gy and a recommended 1cc limitation to 20 Gy. The maximum esophageal dose in this group compares favorably to the maximum dose allowed on RTOG 0813 (when converted to 2 Gy fraction equivalents using the linear-quadratic model, the Group 4 Dmax is 80% of the dose allowed on this multicenter protocol).

The doses constraints chosen for Group 4 have clinical relevance for patients undergoing spine SBRT for metastatic renal cell carcinoma – these tumors are prescribed to receive a single fraction dose of 24 Gy, yet, for lesions adjacent to the esophagus, tumor coverage must sometimes be compromised to respect our current esophageal maximum of 16 Gy. Thus, prospective validation of higher esophageal tolerances would allow improved tumor coverage, with expected improvement in tumor control.

Table 3. Esophageal Dose Constraints for single fraction treatments (Gy).

* = recommended, but not mandated.

Stage	Patient Group	< 5cc	<1cc*	<0.01 cc
Stage 1	Group 1	12	14	16
	Group 2	12	14	16
Stage 2	Group 3	14.5	17	19
	Group 4	18	20	22

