6.0 Evaluation During Study

Following treatment, patients will be evaluated in follow-up visits at months, 3 (+/- 2 weeks), 6 (+/- 4 weeks), 9 (+/- 4 weeks), 12 (+/- 8 weeks), 18 (+/- 8 weeks) 24 (+/- 8 weeks), and annually thereafter. Additional follow-up visits may be scheduled as needed in the judgment of the attending physician.

Toxicity will be monitored and recorded as per the NCI Common Terminology Criteria for Adverse Events (CTACE) version 4.0. Specific esophageal toxicity endpoints to be monitored include: dyspepsia, dysphagia, fistula, hemorrhage, necrosis, obstruction, pain, perforation, stenosis, ulcer, varices and esophagitis. Additional workup of esophageal symptoms (e.g., endoscopy, swallowing evaluation) will be at the discretion of the treating physician. Additional systemic agents or subsequent radiation therapy to the esophagus in the course of treatment will be recorded at each follow-up.

While acute esophagitis is not the primary parameter to be monitored, this protocol will also assess transient effects of spinal SBRT. Patients will complete MD Anderson Symptom Inventory (MDASI), with inclusion of the MDASI lung module, which has been previously used to assess acute esophagitis during thoracic chemoradiation therapy (41), at baseline and then weekly for four weeks following treatment. The MDASI spine module will also be incorporated into the questionnaire. Patients in Groups 1, 3, and 4 will also be asked to score use of antacids or anti-reflux medications at baseline and weekly for four weeks following treatment. Changes in patient medications (e.g. prescription of corticosteroids) at the time of spinal radiation therapy will be recorded.

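### Sections 5.1 and 6.0 still tie the standard-constraint esophageal reference and the antacid scoring to Group 1, which is closed at five patients; Group 6 should be named in both places

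*Combined protocol and SAP*

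**What the plan says.** Section 5.1 gives Group 1 two tasks. The first is dosimetric: "The data collected from Group 1 in the first stage of the protocol will give us data on the dose delivered to the esophagus" under current guidelines. The second is that these data "will serve to verify the safety of our current practice".

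The same section closes accrual to "Groups 1 (T4-T12 with fiducials) and 2 (L1-L5 with fiducials) and begin enrollment in three new groups of 10 patients each". The new groups are Group 5 (C5-T3), Group 6 (T4-T12) and Group 7 (L1-L5). Of Stage 1 as a whole it says: "In this stage of the study patients will be treated with the standard dose constraints to normal tissues". Section 2.3 gives the count at this revision: "we have accrued 7 patients into Stage 1 of the protocol (five in group 1, and two in group 2".

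Section 6.0 restricts one item by group: "Patients in Groups 1, 3, and 4 will also be asked to score use of antacids or anti-reflux medications at baseline and weekly". These scores continue through the fourth week after treatment. The esophageal toxicity list and the MDASI with its lung module, in the same section, carry no group restriction. Section 8.0 (Analysis) summarizes Dmax, D5cc, central lumen dose and full thickness dose, and tabulates adverse events, for every patient group.

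On comparability, section 5.5.1 says that in Stage 1 "patients dispositioned to undergo single and multi-fraction treatments will be enrolled", whereas Stage 2 takes single-fraction patients only. Stage 2 is limited to T4-T10 (section 5.1) and has further exclusions (section 3.3) that do not apply to Stage 1.

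**The concern.** Stage 2 relaxes the esophageal constraints in two groups of ten. To read its results, one needs to know what dose, symptoms and medication use look like at standard constraints. The plan assigns that role to a group that can no longer grow and leaves its open successor at the same levels unnamed. Section 5.1 appears not to have been fully updated when the fiducial component was removed. Table 3 likewise stops at Group 4, and section 8.0 still allows Group 2 to accrue although section 5.1 closes it.

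The antacid item matters most because it is collected prospectively each week and cannot be rebuilt later. Mild effects are also where Stage 2 is likely to be informative. Any Grade 3+ esophageal event ends accrual, section 9.0 requires documentation only of treatment-related toxicity of Grade 2 or above, and section 8.0 itself argues that acute toxicity foreshadows late toxicity.

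**Working it through.** **Plan's own figures.** The only power statements are in section 8.0 (Sample Size), for n = 10 and two-sided alpha 0.05.
- Paired difference of 1 SD: noncentral t with 9 df and noncentrality √10 = 3.16 gives 80.3% (stated 80%).
- Correlation of 0.80: Φ(atanh(0.8)·√7 − 1.96) = Φ(0.95) = 82.8% (stated 82%).

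Both reproduce. Both concern fiducial set-up against standard practice, so neither covers the esophageal reference.

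**Inputs.** Group 1 has 5 patients (section 2.3). Group 6 has a target of 10 (section 5.1). A benchmark Grade 3+ rate of 11% comes from the lung radiotherapy series in section 8.0 (74/652 = 11.3%). The plan expects spinal SBRT to be well below that rate.

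**Where each kind of reference data stands for Group 6**

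| Item | Collected or summarized in Group 6? | Source | Defect |
|---|---|---|---|
| Esophageal dose | Yes | 8.0 Analysis | Not named as reference |
| Adverse events | Yes | 6.0, 8.0 Analysis | Not named as reference |
| MDASI with lung module | Yes, no group limit | 6.0 | Not named as reference |
| Weekly antacid score | No | 6.0 | Data not collected |

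**Size.** Three formulas, for n usable reference patients:
- Upper one-sided 95% limit if no Grade 3+ event is seen: 1 − 0.05^(1/n). The two-sided version uses 0.025.
- Chance of at least one event at a true rate of 11%: 1 − 0.89^n.
- 95% CI half-width for a mean dose parameter, in SD units: t(0.975, n−1)/√n.

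| n | Upper limit, one-sided (two-sided) | Chance of ≥1 event at 11% | CI half-width |
|---|---|---|---|
| 3 | 63.2% (70.8%) | 29.5% | 2.48 SD |
| 5 (Group 1 alone) | 45.1% (52.2%) | 44.2% | 1.24 SD |
| 10 | 25.9% (30.8%) | 68.8% | 0.72 SD |
| 15 (all of Groups 1 and 6) | 18.1% (21.8%) | 82.6% | 0.55 SD |

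Five patients would miss a true 11% rate with probability 0.89^5 = 56%.

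**Matching.** Both Group 1 and Group 6 include T11-T12 and multi-fraction patients, and neither is subject to section 3.3. The documents do not say how many patients meet the Stage 2 criteria. The rows for n = 3 and n = 10 therefore show a range, and n = 15 is a ceiling. The matched part of Group 1 may itself be below five.

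**Antacid scores at standard constraints.** As written: at most 5 patients, none newly enrolled. With Group 6 added: at most 5 + 10 = 15.

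**The case against.** A reader might infer that Stage 2 has almost no reference data, or that any rise in esophageal symptoms could be set only against five patients. The documents do not support that. Groups 5-7 are treated at standard constraints, section 8.0 already reports esophageal dose and adverse events by group, and section 6.0 applies toxicity monitoring and the MDASI to all patients. Section 6.0 introduces the MDASI lung module as a tool already used for acute esophagitis. Section 6.0 also records medication changes around radiation in all groups. That is a partial backstop for the antacid item, but it is not a baseline-and-weekly score.

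A reader might also infer that a test or a safety rule is weakened. The plan contains no formal comparison of Stage 2 with Group 1. The stopping rule is absolute, and the safety rationale in section 8.0 rests on the lung series, the institution's earlier prospective data and the published reports. Section 6.0 also says that acute esophagitis is not the main parameter monitored.

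Finally, the 45% and 18% limits assume that no event occurs; the documents report no toxicity result for Group 1. Moving from 45% to 18% would come mostly from naming data that will exist anyway.

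All of this stands, and it narrows the point. It does not remove the out-of-date reference in section 5.1 or the missing antacid scores.

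**Conclusion.** The point holds in a limited form. For dose, adverse events and MDASI, the fault is that section 5.1 names a closed group of five and not the open group at the same levels. For antacid and anti-reflux use, concurrent standard-constraint data are actually lost. The consequence is for the descriptive interpretation of Stage 2 and for the statement that Group 1 will confirm the safety of current practice. With no Grade 3+ event, five patients are compatible with a rate of up to 45% (one-sided 95%), which confirms little.

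The 18% limit for Groups 1 and 6 together assumes full accrual of Group 6, no event, and all 15 patients usable. It should not be read as what the matched reference will deliver; restriction to comparable patients will raise it by an amount the documents do not allow one to compute. The count of five assumes that nobody joined Group 1 between the tally in section 2.3 and its closure.

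The change is worth making while Group 6 is enrolling, because unscored weeks cannot be recovered.

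**What to change.** **Section 5.1.** Name Groups 1 and 6 together as the standard-constraint reference. Report them separately by treatment platform, since section 2.3 describes a move to a new accelerator. Make the primary reference the subset that meets the Stage 2 criteria: T4-T10, single fraction, and none of the section 3.3 exclusions. Those exclusions cover earlier radiation to the treated level or to the esophagus, pre-existing esophageal disease, and disease arising in the posterior elements. The esophageal-disease exclusion bears directly on antacid use. State the size of this subset wherever its results are reported.

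**Section 6.0.** Change the antacid list to Groups 1, 3, 4 and 6. Group 1 stays so that its existing scores remain covered. Group 5 (C5-T3) may be added, but its levels do not overlap T4-T10, so it would be supplementary only.

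**Cost.** A few words in two sections, and one short item at five time points (baseline plus four weekly) for about 10 patients who already complete the MDASI at those times. No treatment, sample size or stopping rule changes.

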5.2 Treatment summary

All patients will receive CT-guided spinal SBRT using intensity modulated radiation therapy to maximize the conformality of the treatment plan to the target volume, while sparing normal structures.

5.3 Simulation

For simulation and treatment, we will employ our previously described SBRT setup (14), using a stereotactic BodyFix cradle. At the time of simulation, patients may be administered barium sulfate oral contrast (40) to aid in delineation of the esophagus on axial imaging. A CT dataset will be acquired for treatment planning – a four dimensional CT using optical respiratory monitoring is recommended.

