1.0 Objectives

- 1.1 Assess the use of implanted fiducial markers in the treatment planning and delivery workflow for frame-based spinal stereotactic body radiation therapy (spinal SBRT).
- 1.2 Characterize the six-dimensional set-up accuracy of the ExacTrac patient positioning system as applied to spinal SBRT for lesions of the thoracic and lumbar spine.
- 1.3 Establish whether the addition of implanted gold seed fiducials enhances the ability of the ExacTrac system to detect and correct patient position relative to image fusion based solely on bony anatomy.
- 1.4 Characterize the radiation dose delivered to organs at risk (OARs) when accounting for intrafraction OAR motion through the use of 4 dimensional CT simulation for treatment planning.
- 1.5 Characterize the radiation tolerance of the normal esophagus to large-fraction radiation treatment through dose constraint relaxation.

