Overall, the current state of the clinical literature highlights the need for high quality data for esophageal toxicity in the setting of large dose hypofractionated radiation therapy. Taken together, these reports indicate that, in current practice, SBRT is exceptionally well-tolerated with respect to the esophagus, and suggest that current practice may reflect overly conservative esophageal dose constraints. In the setting of spinal SBRT, while primarily driven by the spinal cord tolerance, esophageal dose constraints can be another significant factor forcing clinicians to compromise CTV coverage for fear of inducing esophageal toxicity.

Interestingly, while a significant portion of SBRT data come from respiratory gated four dimensional (4D) CT based treatment of lung tumors, the question of how organ motion should be incorporated into setting dose constraints for normal tissues has been largely ignored. A prior

study of esophageal motion in 29 patients using 4D CT demonstrated a substantial degree of esophageal motion, noting that 9 mm and 8 mm margins respectively would have been necessary to incorporate all movement of the distal esophagus in the medio-lateral and dorso-ventral directions (39).

Given that the current state of SBRT practice thus relies on esophageal constraint parameters which a) may unnecessarily force compromise of CTV coverage through overly strict constraints and b) do not account for organ motion, the second major goal of this protocol is to employ our fiducial-enhanced, 4DCT based, treatment platform to prospectively collect high-quality data on esophageal dose tolerance through careful constraint relaxation.

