5.4 Organ at risk delineation

For treatment planning purposes, contouring of normal structures will be performed on the “average” CT dataset. For assessment of OAR motion, the data analysis will involve re-contouring at each phase of the respiratory cycle.

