5.5.2 Non-esophageal dose constraints

With the exception of esophageal dose, treatment planning will be based on our group's current standards for organ-at-risk (OAR) dose constraints; however the final target volume and treatment plan will be at the discretion of the attending physician. Treatment planning will be carried out using the "average" image stack if a 4D CT data set is used.

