We will use descriptive statistics to summarize the demographic and clinical characteristics of patients enrolled in this study. We will similarly summarize Dmax, D5cc, central lumen dose, and full thickness dose for each patient group (defined above).

We will use the methods of Bland and Altman (43) to compare the positioning of the isocenter with respect to 6 directional orientations (superior-inferior, anterior-posterior, lateral-medial, pitch, roll, and yaw) using the implanted fiducial markers and using our standard practice for each patient group. We will similarly compare the 3-dimensional distance from the isocenter as calculated using the implanted fiducial markers and using our standard practice. We will also estimate these paired differences (fiducial – standard practice) with 95% confidence intervals, and we will estimate with 95% confidence intervals the correlation between the measures made using the fiducial markers and those made using standard practice. We will similarly analyze Dmax, D5cc, central lumen dose, and full thickness dose for each patient group.

We will tabulate adverse events by grade for each patient group.

Sample Size

We will test whether the paired difference (fiducial – standard practice) in 3-dimensional distance from the isocenter is significantly different from 0. A sample size of 10 patients in each patient group will give us 80% power to detect an effect size of 1 standard deviation with a 2-sided significance level of 0.05. A sample size of 10 patients will also give us 82% power to

detect a correlation between the 2 methods of estimating the position of the isocenter of at least 0.80 using a 2-sided significance level of 0.05. These sample size calculations were performed with nQuery Advisor ® 7.0 (Copyright © 1995-2007, Statistical Solutions, Saugus, MA).

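### Organ-motion dose (Objective 1.4) depends on 4D CT that no patient is required to have, and the dose analysis in Section 8.0 contains no comparison that measures motion

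*Combined protocol and SAP*

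**What the plan says.** **Where 4D CT is relied on.** Objective 1.4 (Section 1.0) is to characterize organ-at-risk dose when "accounting for intrafraction OAR motion through the use of 4 dimensional CT simulation for treatment planning". Section 2.2 criticizes existing esophageal constraints for ignoring organ motion and answers with a plan to "employ our fiducial-enhanced, 4DCT based, treatment platform" for the tolerance data. Section 5.1 expects Stage 1 to show how far organ motion matters at each spinal level. Section 5.4 contours on the average CT and says that, for motion, "the data analysis will involve re-contouring at each phase of the respiratory cycle".

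**Where it is optional.** Section 5.3: "a four dimensional CT using optical respiratory monitoring is recommended". Section 5.1: "Four dimensional CT datasets are recommended for simulation". Section 5.5.2 plans on the average "image stack if a 4D CT data set is used".

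**What is analysed.** Section 7.0 defines four esophageal dose parameters (Dmax, D5cc, central lumen dose, full-thickness dose) and will correlate esophageal events with them. Section 8.0 first summarizes them descriptively by group. It then sets out Bland-Altman methods, paired differences and correlations for fiducial versus standard-practice positioning, and adds: "We will similarly analyze Dmax, D5cc, central lumen dose, and full thickness dose for each patient group".

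**The concern.** A stated objective should have data that the protocol secures and an analysis that answers it. Here both are loose.

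On data, phase-by-phase contouring cannot be done without a 4D data set, and no section says who must have one, how many are needed, or how patients without one are handled.

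On analysis, the paired comparison extended to the dose parameters contrasts two ways of aligning the patient. It does not contrast dose with and without respiratory motion. Sections 2.3 and 5.1 close Groups 1 and 2, remove fiducials and enroll Groups 5 to 7 without them, so the pair cannot be formed in patients enrolled from then on.

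At stake are Objective 1.4, the Stage 1 question of where motion matters, and the claim in Section 2.2 that the esophageal tolerance data will improve on constraints that ignore motion.

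**Working it through.** **Step 1: set the sections side by side.**

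| Section | Status of 4D CT |
|---|---|
| 1.0 (Objective 1.4) | the means of meeting the objective |
| 2.2 | the basis of the platform for tolerance data |
| 5.4 | assumed: average data set and respiratory phases, no condition |
| 5.1, 5.3 | recommended |
| 5.5.2 | conditional |

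Sections 5.4 and 5.5.2 do not agree. The first takes an average data set for granted; the second ties it to a 4D scan having been used.

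**Step 2: look for a motion contrast.** Section 5.4 yields contours by phase. Section 7.0 defines the dose parameters without saying whether they are planned or motion-inclusive. Section 8.0 gives a descriptive summary and one paired contrast, fiducial minus standard practice. Section 2.3 reports seven patients accrued to Groups 1 and 2. In them the pair may exist, but it still concerns alignment. No section defines a motion-inclusive dose or compares it with the average-CT dose.

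**Step 3: reproduce the plan's own figures.** Section 8.0 states 80% power for a paired difference of 1 SD with n = 10 and two-sided alpha 0.05.
- Paired t-test: 9 df, critical t = 2.262, noncentrality 1 × √10 = 3.162, power 80.3%. This agrees.
- Correlation of 0.80, stated power 82%, by Fisher's z: atanh(0.80) × √(10 − 3) − 1.960 = 1.099 × 2.646 − 1.960 = 0.947, and Φ(0.947) = 82.8%. This agrees closely.

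Both figures concern the fiducial comparison. None is stated for organ motion.

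**Step 4: what incomplete uptake would cost.** Uptake is not in the documents, so the range is an assumption. The half-width of a 95% confidence interval for a mean paired difference, in SD of the differences, is t(0.975, n − 1)/√n. For example, 2.262/√10 = 0.715, 2.365/√8 = 0.836 and 2.776/√5 = 1.242.

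| Patients of 10 with 4D CT | Half-width (SD) | Power for 1 SD |
|---|---|---|
| 10 | 0.715 | 80% |
| 9 | 0.769 | 75% |
| 8 | 0.836 | 68% |
| 6 | 1.049 | 51% |
| 5 | 1.242 | 40% |

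If each patient has the scan independently with probability u, the chance that all 10 in a group have it is u¹⁰: 35% at u = 0.9, 11% at 0.8 and 0.1% at 0.5.

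**The case against.** The best defence is that Objective 1.4 says characterize. It promises no test, and the descriptive summary in Section 8.0 needs no fiducials and suits that verb. Phase-by-phase contouring is a stated motion procedure. A recommendation may be followed in every patient, and leaving the scan optional may be a deliberate trade-off against imaging dose and scan time. The Table 3 constraints and the toxicity stopping rule also work without 4D CT.

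Much of this stands, and it limits what can be claimed. A reader might go further in four ways that the documents do not support:

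- *That motion dose will exist only in a subset picked by clinicians according to level or expected motion.* No section says who chooses, on what grounds, or how often. Uptake could be complete.
- *That toxicity will be correlated with doses measured in two different ways.* If planned dose is used for everyone, this does not arise. Section 7.0 simply does not say. A smaller mismatch, average-of-4D against plain CT planning sets, could follow from Section 5.5.2.
- *That motion outweighs set-up error because Section 2.2 cites 8 to 9 mm and Section 2.1 cites 2 mm.* The first is a margin covering all movement of the distal esophagus; the second is a translational set-up error. They are not comparable dose effects.
- *That Objective 1.4 itself promises results by spinal level.* That aim is in Section 5.1.

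What the defence does not answer is that the descriptive summary never says which dose it summarizes, and that nothing turns the phase contours into a dose or a comparison.

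**Conclusion.** The point holds in this form: motion data are assured for no patient, their selection is uncontrolled, no motion-inclusive dose is defined, and the one paired dose analysis cannot be formed in patients without fiducials and would not address motion if it could. The need for a planned-versus-motion comparison comes from Sections 2.2 and 5.1 more than from the wording of Objective 1.4.

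The analysis gap is certain from the text. The loss of precision is conditional on uptake: none if every patient is scanned, and a half-width rising from 0.72 SD to 0.84 SD or 1.24 SD if 8 or 5 of 10 are. Any selection bias would come on top and cannot be sized from the documents. The sponsor should correct this. It does not undermine the constraint levels or the toxicity monitoring as such.

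**What to change.** **1. Analysis (the stronger and cheaper part).** In Section 8.0, replace the sentence on analysing the dose parameters similarly with a paired comparison, with 95% confidence intervals, of dose on the average CT against dose from the phase-by-phase contours of Section 5.4. Include every patient with a 4D data set, and report by group or spinal level. Ten patients spread over T4 to T12 (nine levels) is about one per level, so group is the realistic unit. Define in advance how the phase contours become one motion-inclusive value per patient. State in Section 7.0 that the toxicity correlation uses one dose definition, the planned dose, for all patients, with motion-inclusive dose as a secondary analysis.

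**2. Data.** Reconcile Sections 5.1, 5.3 and 5.5.2 with Sections 1.0, 2.2 and 5.4, by one of two routes:
- make 4D CT the default in all groups contributing to Objective 1.4, including Groups 5 and 7 if results are reported by level, and record the reason for each omission; or
- keep it optional, report uptake and reasons by group, compare patients with and without it, and limit the motion conclusions to where scans exist.

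**Cost.** Amendment wording and extra dosimetric analysis on contours already planned. The first route also adds some scan time and imaging dose, which is a fair reason to prefer the second.
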